3.1.2. Single-blind Run-In (RI) Period (12 weeks)

During the single-blind RI period, treatment with blinded rilonacept is administered and subjects are weaned off background standard of care (SOC) therapy for their pericarditis disease. Subjects will be blinded regarding the time of transition from the single-blind to the double-blind period; i.e., they will not be aware of the duration of the RI period.

In the single-blind RI period, subjects ≥ 18 years old will receive blinded rilonacept as an initial loading dose of 320 mg (2 SC injections of 160 mg each) at the RI baseline visit (2×2 ml), followed by a 160 mg (2 ml) SC dose once weekly throughout the RI period. Pediatric subjects (≥ 12 and < 18 years old) will receive an initial loading dose of blinded rilonacept 4.4 mg/kg (2 SC injections of 2.2 mg/kg each) at the RI baseline visit (maximum 2×2 ml), and then 2.2 mg/kg (maximum 2 ml) SC once weekly throughout the RI period.

The RI period includes:

- 1-week Stabilization period, during which blinded rilonacept is administered in addition to SOC pericarditis therapy, and the ongoing pericarditis episode is treated.
- 9-week Weaning period, during which subjects are weaned off background SOC pericarditis therapy, as applicable, while treatment with blinded rilonacept continues. The dosages of CS, NSAIDs, and colchicine will be tapered according to the guidelines for weaning in the Pharmacy Manual (for the purpose of the protocol, aspirin is considered an NSAID). In general, CS doses will be tapered off starting at RI Week 1 and will be withdrawn by RI Week 10 (over a total of 9 weeks). NSAID and colchicine doses will be tapered off starting at RI Week 4 and will be withdrawn by RI Week 10 (over a total of 6 weeks).
- 2-week Monotherapy period: Subjects who have been successfully weaned off background SOC pericarditis therapy will continue to receive blinded rilonacept.

Subjects who stopped background pericarditis medications and achieve Clinical Response on rilonacept monotherapy at RI Week 12/RW baseline will proceed into the double-blind placebo-controlled Randomized-Withdrawal (RW) period of the study. For definition of Clinical Response, refer to [Section 6.2.2](#).

Subjects who are unable to achieve Clinical Response on rilonacept monotherapy at RI Week 12/RW baseline are to be discontinued from study drug, transitioned to SOC pericarditis therapy at the Investigator's discretion, and followed through the end of the RW period.

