3.1.3. Double-blind Placebo-controlled RW Period (pericarditis recurrence event-driven duration)

During the RW period, subjects who were able to stop background pericarditis medications and who achieve Clinical Response on rilonacept monotherapy at RI Week 12/RW baseline will be randomized 1:1 to double-blinded administration of study drug:

- Rilonacept 160 mg (or 2.2 mg/kg in pediatric subjects ≥ 12 and < 18 years old) SC injections once weekly OR
- Matching placebo SC injections once weekly

Pericarditis Recurrence in the RW Period: For the definition of pericarditis recurrence, refer to Section 6.2.3.

Upon pericarditis recurrence, subjects who report at least 1 day with pericarditis pain measurement ≥ 4 on the 11-point Numerical Rating Scale [NRS] and have 1 CRP value ≥ 1 mg/dL (either on the same day or separated by no more than 7 days) will receive **bailout rilonacept** (2 open-label injections of 160 mg rilonacept [or 4.4 mg/kg for pediatric subjects]) irrespective of randomized treatment assignment and as soon as at least 5 days have passed since the last study drug injection. The subjects transitioning to bailout rilonacept will remain blinded to their prior RW period treatment assignment. Sequential Oral Rescue Therapy (ORT), i.e., analgesics first, then NSAIDs, and then colchicine, can be added, if needed, at the discretion of the Investigator, as outlined in Section 5.6.3 and detailed in the Pharmacy Manual.

Subjects with pericarditis recurrence who do not meet the protocol criteria for bailout rilonacept will continue blinded study drug until they meet the protocol criteria for bailout rilonacept or through the end of the RW period. For those subjects, sequential ORT can be added to blinded study drug at the discretion of the Investigator, as outlined in Section 5.6.3 and detailed in the Pharmacy Manual.

All suspected pericarditis recurrence events in the RW period will be formally adjudicated by the Clinical Endpoint Committee (CEC), and only events that are confirmed by the CEC as pericarditis recurrences will be used in the Primary Endpoint analysis.

The RW period will continue until the prespecified number of primary efficacy endpoint (CEC-confirmed pericarditis recurrence) events has occurred. Based on projected event accrual and subject randomization, Kiniksa Pharmaceutical will determine the end of the RW period and announce to sites so that subject End of Randomized Withdrawal (EORW) visits

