3.3. Justification for Dose Selection

[REDACTED]
[REDACTED] i.e., 320 mg SC loading dose (4.4 mg/kg in subjects ≥ 12 and < 18 years old), followed by once-weekly SC doses at 160 mg (2.2 mg/kg in subjects ≥ 12 and < 18 years old).

In the rilonacept development program in CAPS, gout, rheumatoid arthritis, and other inflammatory conditions, over 2000 subjects were exposed to rilonacept, including 1650 subjects receiving a rilonacept dose of 160 mg or higher. A total of 103 and 169 subjects were exposed to any rilonacept dose for at least 1 year or 6 months, respectively. Most of the real-life experience with rilonacept comes from the CAPS population treated at this marketed dose. As of March 2018, approximately 365 CAPS patients have been exposed to rilonacept in the post-marketing setting since 2008. The safety data accumulated so far support the benefit/risk ratio for the rilonacept dose intended to be evaluated in subjects with recurrent pericarditis.

Based on the clinical data with rilonacept from the Phase 2 proof of concept study (KPL-914-C001), it is expected that rilonacept doses [REDACTED] (320 mg followed by 160 mg SC once weekly and corresponding pediatric doses), and evaluated in the KPL-914-C001 study, will consistently provide adequate suppression of clinical inflammatory response, including CRP levels, in patients with recurrent pericarditis.

Subjects who meet the protocol criteria for **bailout rilonacept** upon pericarditis recurrence in the RW period of the study (Sections 3.1 and 6.2.3), irrespective of treatment assignment at randomization, will receive open-label rilonacept (loading dose of 320 mg SC followed by once-weekly SC injections of 160 mg, or the corresponding pediatric doses). [REDACTED]

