5.2.2. Pediatric Subjects (≥12 and <18 years old)

Rilonacept: Loading dose 4.4 mg/kg administered as 2 SC injections, 2.2 mg/kg each (maximum 160 mg each) at RI baseline, followed by once-weekly SC injections of 2.2 mg/kg (maximum 160 mg). The volume of injections will be based on the subject's weight (Table 1).

Placebo (in RW): once-weekly SC injections with volume based on the subject's weight (Table 1 , maximum 2 ml).

Upon meeting protocol criteria for bailout rilonacept (Sections 3.1 and 6.2.3) in the RW period, subjects will be transitioned to open-label rilonacept 4.4 mg/kg administered as 1 (maximum 2 ml) or 2 SC injections at the next scheduled study drug administration date, followed by once-weekly SC injections of 2.2 mg/kg (maximum 2 ml). The volume of injections will be based on the subject's weight (Table 1).

Study drug dose/volume will be calculated by the Investigator or pharmacist during site clinic visits based on body weight (as specified in Section 13.1) using a weight-based dosing chart in kilograms (Table 1).

Table 1: Study Drug Dose Volume (After Reconstitution) by Body Weight in Kilograms for Pediatric Subjects Aged ≥12 and <18 Years

Weight Range (kg)	Loading Dose Volume (ml)	Weekly Dose Volume (ml)
23.6 to 27.2	2 x 0.7	0.7
27.3 to 30.8	2 x 0.8	0.8
30.9 to 34.4	2 x 0.9	0.9
34.5 to 38.1	2 x 1.0	1.0
38.2 to 41.7	2 x 1.1	1.1
41.8 to 45.4	2 x 1.2	1.2
45.5 to 49.0	2 x 1.3	1.3
49.1 to 52.6	2 x 1.4	1.4
52.7 to 56.3	2 x 1.5	1.5
56.4 to 59.9	2 x 1.6	1.6
60.0 to 63.5	2 x 1.7	1.7
63.6 to 67.2	2 x 1.8	1.8
67.3 to 70.8	2 x 1.9	1.9
70.9 or greater	2 x 2.0	2.0

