- m All procedures are to be completed prior to study drug administration.
- n The first dose of study drug is a loading dose. Adult subjects receive 2 SC doses 160 mg (total 320 mg); pediatric subjects (subjects ≥ 12 and < 18 years of age) receive 2 SC doses of 2 x 2.2 mg/kg.
- o Study drug administration is once weekly with a minimum of 5 days required between doses.
- p Randomization and subsequent study drug dispensing to occur after confirmation of Clinical Response (see definition of Clinical Response in Section 6.2.2).
- q The Randomization visit serves as both the RI Week 12 visit and the RW baseline visit.
- s PK and ADA samples will be collected prior to study drug administration. PK at enrollment/baseline will be taken from ADA

Table 3: Study Schedule of Activities – Randomized Withdrawal

Trial Period	RANDOMIZED WITHDRAWAL (event-driven) ^m								END OF RANDOMIZED WITHDRAWAL (EORW) ^t
Visit Name	RW Week 4	RW Week 8	RW Week 12	RW Week 16	RW Week 20	RW Week 24	RW Every 8 Weeks	RW Every 8 Weeks	Per Announced End Date ^u /LTE-Baseline
Visit Window ^b (days)	+/- 2	+/- 2	+/- 2	+/- 2	+/- 2	+/- 2	+/- 2	+/- 2	+/- 7
Visit Type	TC/RN	Clinic	TC/RN	Clinic	TC/RN	Clinic	TC/RN	Clinic	Clinic
Informed Consent Form									X
Concomitant medications	X	X	X	X	X	X	X	X	X
Pericarditis Concomitant medications	X	X	X	X	X	X	X	X	X
Full Physical Examination ^e						X			X
Abbreviated Physical Examination ^d									
Body weight and height		X		X		X		X	X
12-Lead ECG						X			X
Echo ^e						X ^e			X ^e
MRI (substudy only)						X			
Pericardial pain (11-point NRS)	DAILY								
EQ-5D						X			X
SF-36						X			X
ISI						X			X
PGIPS		X		X		X		X	X
PGA-PA		X		X		X		X	X
Hematology, Chemistry Labs (Central)		X				X		X	X
Lipid Panel (Central) ^h						X			X
CRP (Local)									

Trial Period	RANDOMIZED WITHDRAWAL (event-driven) ^m								END OF RANDOMIZED WITHDRAWAL (EORW) ^t
	RW Week 4	RW Week 8	RW Week 12	RW Week 16	RW Week 20	RW Week 24	RW Every 8 Weeks	RW Every 8 Weeks	Per Announced End Date ^u / LTE-Baseline
Visit Window ^b (days)	+/- 2	+/- 2	+/- 2	+/- 2	+/- 2	+/- 2	+/- 2	+/- 2	+/- 7
Visit Type	TC/RN	Clinic	TC/RN	Clinic	TC/RN	Clinic	TC/RN	Clinic	Clinic
CRP(Central)	X	X	X	X	X	X	X	X	X
PK (Central) ^s		X				X			X
ADA (Central) ^s						X			X
Biomarkers (Central)		X				X			
Urine Pregnancy ^j (Local or Central)									X
Urinalysis									X
IWRS Subject Status Update									X
IWRS Weight Input (pediatric only)		X		X		X		X	X
IWRS Drug Dispensing		X		X		X		X	X ^v

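### Footnote n of the Schedule of Activities, read literally, states a paediatric loading dose of 8.8 mg/kg against 4.4 mg/kg elsewhere; the bailout injection count also differs between sections

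*Protocol*

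**What the plan says.** All references are to Protocol Version 3.0 (Amendment 2).

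**Run-in loading dose.** In Table 2 of Section 13.1, the row for in-clinic study drug administration carries footnote n at the run-in baseline visit. For adults the footnote reads "Adult subjects receive 2 SC doses 160 mg (total 320 mg"; in the same sentence, paediatric subjects "receive 2 SC doses of 2 x 2.2 mg/kg". The paediatric clause gives no total, no maximum and no pointer to the dosing table.

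Elsewhere:

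- Section 5.2.2: "Loading dose 4.4 mg/kg administered as 2 SC injections, 2.2 mg/kg each (maximum 160 mg each) at RI baseline".
- Section 3.1.2, with the same figures in the synopsis: "4.4 mg/kg (2 SC injections of 2.2 mg/kg each) at the RI baseline visit".
- Section 3.3: "320 mg SC loading dose (4.4 mg/kg in subjects" aged 12 to 17.
- Section 5.2.3: the loading dose consists of two injections, for adults and paediatric subjects alike.
- Table 1 in Section 5.2.2: every loading entry is two times the weekly volume for that weight band.

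**Bailout dose.** The synopsis and Section 3.1.3 give "2 open-label injections of 160 mg rilonacept [or 4.4 mg/kg for pediatric subjects"]. Section 5.2.2 gives "open-label rilonacept 4.4 mg/kg administered as 1 (maximum 2 ml) or 2 SC injections" and refers to Table 1 for volumes.

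**The concern.** Footnote n is dosing text, not background. It is attached to the visit at which the loading dose is given, and Section 6.1.2, which describes that visit, contains no dosing instruction and sends the site to Section 13.1. A site that took the footnote at face value would arrive at a figure that the rest of the protocol contradicts, in subjects aged 12 to 17. Paediatric enrolment is limited to 20% of the study population, so with up to about 100 enrolled the ceiling is about 0.20 x 100 = 20 subjects.

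The contradiction also blurs a safety rule. Section 5.5 defines an overdose as a dose above the one the protocol describes and has it reported by the SAE procedure. With two descriptions of the same dose in force, that threshold is unclear for minors.

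The bailout text raises a smaller question: how many injections a paediatric subject receives. Section 3.1.4 relies on Section 3.1.3 again when rilonacept is resumed in the extension, so the wording is used in more than one period.

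**Working it through.** **Inputs.** Per-injection dose 2.2 mg/kg and maximum 160 mg (Section 5.2.2); two injections (Sections 3.1.2, 5.2.2 and 5.2.3); concentration 80 mg/ml and at most 2 ml withdrawn per vial (Section 5.3); volumes by weight band (Table 1); footnote n (Section 13.1).

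**Step 1: reproduce the stated figure.** 2 x 2.2 = 4.4 mg/kg. This matches Section 5.2.2.

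**Step 2: check Table 1 against it.** Loading dose in mg = 2 x volume x 80. In the lowest band (23.6 to 27.2 kg), 2 x 0.7 x 80 = 112 mg, and at the midpoint of 25.4 kg this is 112 / 25.4 = 4.41 mg/kg. Every closed band gives 4.40 to 4.41 mg/kg at its midpoint, with 4.12 to 4.75 mg/kg across the band limits. Table 1 is therefore consistent with 4.4 mg/kg and not with 8.8 mg/kg.

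**Step 3: read footnote n literally.** The adult clause reads two SC doses of 160 mg, total 320 mg, so an SC dose is one injection. Applying the same construction to the paediatric clause gives 2 x (2 x 2.2) = 8.8 mg/kg. Ratio: 8.8 / 4.4 = 2.0.

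**Step 4: apply the 160 mg per-injection maximum.** On the literal reading each injection is 4.4 mg/kg, which reaches 160 mg at 160 / 4.4 = 36.4 kg. Above that weight the capped total stays at 320 mg while the Table 1 dose goes on rising.

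| Weight | Table 1 | Footnote n, no maximum | Footnote n, 160 mg maximum | Capped / Table 1 |
|---|---|---|---|---|
| 23.6 kg | 2 x 0.7 x 80 = 112 mg | 8.8 x 23.6 = 208 mg | 208 mg | 1.86 |
| 50 kg | 2 x 1.4 x 80 = 224 mg | 8.8 x 50 = 440 mg | 320 mg | 1.43 |
| 70.9 kg | 2 x 2.0 x 80 = 320 mg | 8.8 x 70.9 = 624 mg | 320 mg | 1.00 |

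The ratio at 23.6 kg is below 2 only because Table 1 rounds up at the bottom of the band (112 mg against 4.4 x 23.6 = 104 mg).

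**Step 5: bailout.** The synopsis and Section 3.1.3 say two injections. Section 5.2.2 says one, of up to 2 ml, or two. Table 1 lists loading volumes only as two injections. The combined Table 1 volume is 2.0 ml or less only in the four lowest bands (2 x 0.7, 2 x 0.8, 2 x 0.9 and 2 x 1.0 ml, up to 38.1 kg), so the single-injection option could arise only there, and Table 1 does not show it.

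**The case against.** The best reply is that footnote n is shorthand and the only outlier. It can be read as two SC doses, that is, 2 x 2.2 mg/kg, which conflicts with nothing. Section 5.2.2 requires the investigator or pharmacist to calculate the dose from the weight chart in Table 1, and the schedule has rows for paediatric weight input and drug dispensing through the IWRS. Further preparation detail is left to the Pharmacy Manual. At 50 kg the literal reading needs 220 / 80 = 2.75 ml per injection, more than the 2 ml that a vial yields, so a site would probably notice.

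Much of this stands. It makes a misdose unlikely, and nothing in the protocol suggests that a second regimen was planned. It does not remove the contradiction: the benign reading has to be supplied from elsewhere, because the paediatric clause, unlike the adult one, gives no total.

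Three stronger inferences are tempting and not supported:

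- That a 50 kg adolescent would receive 440 mg instead of 220 mg. This ignores the 160 mg maximum of Section 5.2.2; footnote n's silence on a maximum does not cancel it.
- That the bailout text also doubles the dose. The bracket in Section 3.1.3 sits where the per-injection dose sits, but Section 5.2.2 gives 4.4 mg/kg as the amount delivered in one or two injections, and Section 3.3 speaks of the paediatric dose corresponding to the 320 mg load. Read together, 4.4 mg/kg is the total, and only the injection count differs.
- That run-in safety, PK or response data would be contaminated. This requires a site to follow the footnote over Table 1, and the document gives no sign that any did.

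**Conclusion.** The point holds as an internal contradiction in operative dosing text for minors. Footnote n, read literally, states 8.8 mg/kg with no maximum; Sections 3.1.2, 3.3 and 5.2.2, the synopsis and Table 1 state or imply 4.4 mg/kg. The factor is 2 without a maximum. With the maximum of Section 5.2.2 it falls above about 36.4 kg, to 1.43 at 50 kg and 1.00 from 70.9 kg. The pattern suggests a duplicated multiplier, but that is an inference; which figure is intended is for the sponsor to confirm.

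The paediatric bailout wording is separately inconsistent on the number of injections, though not on the total.

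The sizes rest on the literal reading of the footnote and on the 80 mg/ml concentration in Section 5.3. The primary endpoint, the event target and the analyses are not touched.

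**What to change.** Reconcile footnote n of Table 2, the synopsis, Sections 3.1.2, 3.1.3 and 5.2.2, and Table 1, so that for both the run-in loading dose and the bailout dose the total, the number of injections and the per-injection maximum are stated identically. Where one place is meant to govern, the others should refer to it. If a single bailout injection remains an option, Table 1 and Section 3.1.3 need to show it; if not, Section 5.2.2 needs to change. The sponsor should confirm the intended figures, and the Pharmacy Manual should be checked against them.

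The cost is a clarification letter to sites now and a wording correction in the next amendment. Sample size, endpoints and analysis do not change.

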6.1.2.9 Randomization (RI Week 12/RW Baseline): Clinic Visit

The following assessments and procedures are conducted at the RI Week 12 visit, **prior to randomization**:

- CRP assessment (local and central) (the POC device provided for the study is the preferred method for local laboratory CRP assessment).
- Obtain a pericarditis pain NRS average score for the prior 7 days, including the day of the visit (4 missing NRS values within this week may result in an inability to move forward with randomization).

- Acquire a 12-lead ECG.
- Acquire and submit a cardiac ECHO to the core laboratory per the core laboratory imaging guidelines; ECHO is read locally prior to submission to the core lab.
- Abbreviated physical examination, height and body weight.
- For subjects ≥ 18 years, complete on their device SF-36, EQ-5D-5L, ISI.
- For all subjects, complete the PGIPS score.
- The investigator is to complete the PGA-PA.
- Obtain central laboratory samples for chemistry, hematology, lipid panel, PK, and ADAs.
- Evaluate concomitant medications including pericarditis concomitant medication.
- Assess for AEs.
- Obtain used and unused study drug vials for study drug compliance evaluation.
- Additional discussion/assessments as needed (i.e., remind the subject about daily pericarditis pain NRS input).
- Assess for Clinical Response (refer to [Section 6.2.2](#)).

For subjects who have successfully completed the RI period and are assessed as achieving Clinical Response at the RI Week 12 visit, the RW baseline visit commences.

The following assessments and procedures are conducted at the RW baseline visit:

- Update the subject status in the IWRS by randomizing the subject in the IWRS.
- Obtain weight for pediatric drug dispensing and dosing ([Table 5–1](#)). Please refer to the pediatric study drug dosing [Table 5–1](#) as well as the [Study Schedule of Activities](#) for subsequent visits with weight assessments for pediatric dosing during RW.
- Dispense study drug and record the amount (number of vials) dispensed.
- Have the subject administer the study drug and record in the diary (if within the study drug window).
- Instruct the subject to bring all medications including used and unused study drug to each clinic visit.
- Instruct the subjects on the process to follow for a pericarditis recurrence event.
- Arrange upcoming visits.

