The rationale for bailout rilonacept treatment upon pericarditis recurrence for subjects who were randomly assigned to placebo is that rilonacept had controlled their disease activity during the RI period; therefore, re-initiation of rilonacept is justified to regain control of pericarditis signs and symptoms upon recurrence. Subjects who were randomly assigned to rilonacept and qualify for bailout rilonacept upon pericarditis recurrence in the RW period were initial responders to rilonacept treatment during the RI period; thus it could be assumed that the loss of response during the RW period could be due to development of resistance to rilonacept due to different mechanisms, e.g., higher IL-1 levels or a change in rilonacept pharmacokinetics (PK)/ pharmacodynamics. Therefore, re-administration of a loading dose of rilonacept may help to restore Clinical Response.

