6.1.4. Pericarditis Recurrence Assessment: Clinic Visit

If a subject experiences symptoms consistent with pericarditis recurrence, he/she should contact the study Investigator immediately for evaluation (including in the LTE). It is possible that a subject may have assessments performed remotely, however, assessments are also expected to be performed at the study site as soon as possible. Required assessments include:

- Evaluate pericarditis pain on the 11-point NRS.
- Evaluate concomitant medications as well as pericarditis concomitant medications.
- Obtain laboratory samples for CRP (local and central) (the POC device provided by Kiniksa Pharmaceuticals is the preferred method for local laboratory CRP assessment).
- Acquire a 12 lead ECG.
- Acquire a cardiac ECHO per core laboratory imaging parameters; this ECHO is read locally for the purpose of pericarditis recurrence assessment and is then submitted to the ECHO core laboratory for central review.
- Perform an abbreviated physical examination, height and body weight.
- For subjects >18 years, complete the SF-36, EQ-5D-5L, ISI.
- For all subjects, complete the PGIPS score.
- The Investigator is to complete the PGA PA.
- Obtain central laboratory samples for PK, ADAs, and biomarkers.
- Other procedures deemed necessary per the Investigator or delegated site personnel (e.g. MRI for sub-study subjects).

Upon having completed the evaluation, if the Investigator makes a clinical diagnosis that the subject is having a pericarditis recurrence event, he/she should contact the [REDACTED] medical monitor to review and confirm that all assessments have been performed and collected. Upon [REDACTED] medical monitor confirmation of completion of the assessment, the Investigator commences as described in Section 6.2.3.

Subjects treated for a pericarditis recurrence event will continue to follow the same visit schedule described for the RW period (Section 6.1.5).

Source documentation including the assessments and evaluations used to confirm a pericarditis recurrence event, are required to be sent to CEC.

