7.7.1. General Methods

Statistical analysis will be performed using SAS[®] software Version 9.4 or later. Continuous variables will be summarized using the mean, the standard deviation, median, minimum value, and maximum value. Time-to-event variables will be summarized using percent censored, event rate, and 25th, 50th, and 75th percentiles with 95% CI, if estimable.

Categorical variables will be summarized using frequency counts and percentages. Data will be listed in data listings.

At each of RI and RW periods and in the LTE, baseline will be the last value before the first dose of study drug within each individual period unless otherwise specified. For change-over-time endpoints in the RW period, by-visit analysis will be performed at each scheduled visit for at least 24 weeks.

The analysis for treatment comparison will be triggered after at least the 22nd CEC-confirmed pericarditis recurrence events have been accrued. At that time, randomization will be closed, and subjects will return to study sites for the EORW visit. At that point study treatment will stop (completing the database for the primary efficacy endpoint analysis), and subjects will either continue into the LTE or complete their study participation. Missing data due to end of RW period will be considered as missing at random. Handling of missing values will be described in the SAP.

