7.7.8. Safety Analyses

Treatment-emergent AEs (TEAEs), defined as AEs that start or increase in severity after the first dose of study drug and before 6 weeks after the last dose of study drug, will be coded to system organ class and preferred term using the most recent version of MedDRA. TEAEs will be analyzed for all subjects combined and by treatment group in the RW period. Further analyses by severity and relationship to study drug as well as analyses of serious TEAEs will be presented.

Descriptive statistics will be used to summarize safety endpoints by visit for all subjects combined in the RI period and by treatment group in the RW period. Two-sided 95% CIs will be presented where meaningful. Data summaries will be displayed for clinical laboratory analyses (including safety laboratory measurements, ADAs, etc.), vital signs measurements, ECGs, and physical examination findings.

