In Clinic Study Drug Administration ^o		X		X		X		X	X ^v
Outpatient Study Drug Administration ^o	X	WEEKLY							
Study Drug Compliance Review	X	X	X	X	X	X	X	X	X
Assessment of Pericarditis Recurrence	X	X	X	X	X	X	X	X	X
Adverse Event Reporting ^l	X	X	X	X	X	X	X	X	X

b Scheduling of visits within visit windows requires cautious planning to ensure there is no interruption to subject evaluation and study drug treatment.

c Full physical examination includes at minimum evaluation of vital signs, head, eye, ear, nose, and throat as well as cardiovascular, dermatological, musculoskeletal, respiratory, GI, genitourinary, and neurological systems. The decision to perform examination of genitourinary system should be guided by clinical judgement.

d Abbreviated physical examination includes at minimum evaluation of vital signs, lung and heart sounds, including evaluation for pericardial rub.

e ECHO is required to be obtained according to the central core lab parameters and then read locally and submitted to the central core lab for separate review and analysis.

h Lipid panels are non-fasting and are to be drawn at a minimum of every 6months during the randomization withdrawal and LTE periods, or more frequently as needed, with mandated evaluations as detailed in the schedule of events.

- j For women of child bearing potential - urine pregnancy testing can be repeated as needed throughout the course of the study and serum pregnancy can be drawn as needed; urine pregnancy is required to be performed at enrollment and 6 weeks after the last dose of study drug.
- l Adverse event reporting begins following the subject providing informed consent.
- m All procedures are to be completed prior to study drug administration.
- o Study drug administration is once weekly with a minimum of 5 days required between doses.
- s PK and ADA samples will be collected prior to study drug administration. PK at enrollment/baseline will be taken from ADA. As required, ADA samples will be collected at EOS, ET, and Unscheduled visits.
- t The EORW visit serves as both the last visit of the RW period and the baseline visit of the LTE period.
- u For all subjects, the final clinic visit of the end of RW period is to be scheduled once the End of the Randomization Withdrawal end date is announced by Sponsor. This includes subjects that are taking blinded study drug, open-label rilonacept, or who have prematurely discontinued study drug.

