- l Adverse event reporting begins following the subject providing informed consent.
- m All procedures are to be completed prior to study drug administration.
- o Study drug administration is once weekly with a minimum of 5 days required between doses.
- s PK and ADA samples will be collected prior to study drug administration. PK at enrollment/baseline will be taken from ADA. As required, ADA samples will be collected at EOS, ET, and Unscheduled visits.
- z The MRI to occur only if the previous MRI was done longer than 6 months ago.
- aa Visit to occur 18 months from most recent documented recurrence.
- bb Samples collected every 24 weeks.

Table 5: Study Schedule of Activities – Supplemental Visits

Visit Name	PERICARDITIS RECURRENCE ASSESSMENT	END of TREATMENT (EOT) ^x	SAFETY FOLLOW UP (SFU) ^y (6 weeks post last dose)
Visit Window ^b (days)	N/A	N/A	+/- 2
Visit Type	Clinic	Clinic	Clinic or TC/RN
Concomitant medications	X	X	X
Pericarditis Concomitant medications	X	X	X
Full Physical Examination ^c		X	
Abbreviated Physical Examination ^d	X		
Body weight and height	X		
12-Lead ECG	X	X	
Echo ^e	X ^e	X	
MRI (substudy only)		X ^z	
Pericardial pain (11-point NRS)	X	X	
EQ-5D	X	X	
SF-36	X	X	

Visit Name	PERICARDITIS RECURRENCE ASSESSMENT	END of TREATMENT (EOT) ^x	SAFETY FOLLOW UP (SFU) ^y (6 weeks post last dose)
Visit Window ^b (days)	N/A	N/A	+/- 2
Visit Type	Clinic	Clinic	Clinic or TC/RN
ISI	X	X	
PGIPS	X	X	
PGA-PA	X	X	
Hematology, Chemistry Labs (Central)		X	
Lipid Panel (Central) ^h		X	
CRP (Local)	X		
CRP(Central	X	X	
PK (Central) ^s	X	X	X
ADA (Central) ^s	X	X	X
Biomarkers (Central)	X	X	
Urine Pregnancy ^j (Local or Central)			X
Urinalysis		X	
IWRS Subject Status Update	X ^s	X	
IWRS Weight Input (pediatric only)	X		
IWRS Drug Dispensing	X		
Study Drug Compliance Review	X	X	
Assessment of Pericarditis Recurrence	X	X	X
Adverse Event Reporting ^l	X	X	X

- b Scheduling of visits within visit windows requires cautious planning to ensure there is no interruption to subject evaluation and study drug treatment.
- h Lipid panels are non-fasting and are to be drawn at a minimum of every 6months during the randomization withdrawal and LTE periods, or more frequently as needed, with mandated evaluations as detailed in the schedule of events.

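### Version 3.0 drops the PK and ADA samples at RI Week 12/RW Baseline without listing the change, leaving pre-withdrawal reference values 8 and 6 weeks old

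*Protocol*

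**What the plan says.** **Version 2.0.** Section 6.1.2.9 instructs sites at the randomization visit: "Obtain central laboratory samples for chemistry, hematology, lipid panel, PK, and ADAs". Table 1–1 (Part 2 of 2) agrees, with a mark for PK and for ADA in the RI Week 12/RW Baseline column.

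**Version 3.0.** The visit-by-visit lists are gone. Sections 6.1.3, 6.5.1 and 6.5.2 refer to the schedule in Section 13.1, so Table 2 alone governs run-in sampling. Its Week 12 column is empty for PK and ADA. Footnote s adds only a PK result from the ADA sample at enrollment: "PK and ADA samples will be collected prior to study drug administration. PK at enrollment/baseline will be taken from ADA".

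**Baseline rule.** Section 7.7.1 sets a default for each period: "baseline will be the last value before the first dose of study drug within each individual period unless otherwise specified".

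**Use of the data.** Section 7.7.8 includes ADA among the laboratory summaries, given by visit and by treatment group in RW. Section 3.3 offers, as one possible reason for loss of response in subjects who stay on rilonacept, "a change in rilonacept pharmacokinetics (PK)/ pharmacodynamics".

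**Sampling in RW (Version 3.0).** Table 3 schedules PK at Week 8, Week 24 and EORW, and ADA at Week 24 and EORW. Section 6.1.4 adds at a recurrence visit: "Obtain central laboratory samples for PK, ADAs, and biomarkers". Table 5 also marks ADA at the EOT and safety follow-up visits, and Table 3 footnote s says: "As required, ADA samples will be collected at EOS, ET, and Unscheduled visits".

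**The concern.** In a randomized-withdrawal design, the visit at which subjects either stay on drug or switch to placebo is the natural reference point for exposure and immunogenicity. It is the last moment when every subject is on the same treatment, and a sample missed there cannot be taken later.

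Without it, two questions are harder to answer:

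- **When did ADA arise?** A subject negative at RI Week 6 and positive in RW may have converted on run-in rilonacept or after randomization. The data cannot separate the two. On placebo, the result would be dated to a period in which the subject was off drug.
- **Did exposure change before a recurrence on rilonacept?** Comparing the trough at recurrence with an earlier one needs an earlier one at steady state. Run-in supplies none.

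The summary of changes in Section 13.3 says the move to the sponsor's template altered no study content unless specified. This removal is not specified, so it is either an accidental deletion or an unreported change.

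**Working it through.** **1. The run-in rows side by side**

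| Sample | Version 2.0, Table 1–1 | Version 3.0, Table 2 |
|---|---|---|
| PK | Day 2 (substudy), Weeks 1, 2, 4, **12** | Day 2 (substudy), Weeks 1, 2, 4 |
| ADA | Baseline, Weeks 2, 6, **12** | Baseline, Weeks 2, 6 |

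In Version 3.0 the central hematology/chemistry, lipid and CRP rows keep their Week 12 mark. The visit still has a central blood draw, and a column lost in text extraction is unlikely.

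**2. Age of the default RW baseline at Week 12**

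- PK: 12 − 4 = 8 weeks.
- ADA: 12 − 6 = 6 weeks.
- Interval between scheduled ADA samples for a subject who reaches RW Week 24: 6 + 24 = 30 weeks. With the Week 12 sample it was 24.

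**3. Steady state.** The prescribing information reproduced in the Version 2.0 appendix (its Section 12.3) reports that steady state appeared to be reached by 6 weeks of weekly 160 mg dosing, in patients with CAPS. The last scheduled run-in PK sample is at Week 4. The next is RW Week 8, which in the rilonacept arm comes after 12 + 8 = 20 weeks of dosing.

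**4. Design assumptions (Section 7.4).** Exponential times, placebo median 8 weeks, hazard ratio 0.244, one-sided 2.5%, power 90%, 1:1 allocation, 10% run-in loss. They reproduce the plan's figures:

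- Events = 4(1.960 + 1.282)² / (ln 0.244)² = 42.03 / 1.990 = 21.1, rounded up to 22.
- Enrolment = 50 / 0.90 = 55.6, rounded up to 56.

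**5. Rilonacept-arm recurrences before the first RW PK sample**

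P(recurrence by week t) = 1 − exp(−0.244 × ln 2 × t/8)

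- By Week 8: 1 − 2^(−0.244) = 0.156, or 25 × 0.156 = 3.9 of 25 subjects.
- By Week 16: 1 − 2^(−0.488) = 0.287.
- By Week 24: 1 − 2^(−0.732) = 0.398.

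Of recurrences seen within 24 weeks, 0.156/0.398 = 39% precede the Week 8 sample. Within 16 weeks the share is 0.156/0.287 = 54%.

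**6. ADA frequency.** Section 1.3.1 reports that 30% to 35% of subjects in earlier rilonacept trials were positive at least once. If that held for 50 randomized subjects, 15 to 17.5 would be positive at some time. The documents do not say how many conversions fall between Weeks 6 and 12, so the number misdated could lie anywhere from none up to that total.

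**The case against.** **Stronger readings that the documents do not support**

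- *ADA before RW Week 24 is drawn only at recurrence visits, so sampling follows the outcome.* This is not so. EORW carries an ADA sample for every subject and can precede Week 24, because Version 3.0 dropped the 24-week minimum. EOT, safety follow-up and, as required, unscheduled visits also sample. What is true is that RW has no routine ADA visit before Week 24 or EORW, and Version 2.0 was already the same in this respect.
- *The changed-PK explanation cannot be tested.* RW Week 8 supplies a pre-dose steady-state value in the rilonacept arm. On the design assumptions 84% of that arm is recurrence-free then, and 61% of its recurrences within 24 weeks come later. The test is weakened, not lost.
- *The ADA comparison between arms is biased towards one arm.* ADA arising before randomization occurs on common treatment and is balanced in expectation. By-visit summaries can leave recurrence samples out. Placebo subjects given bailout rilonacept have mixed exposure in later ADA samples, and a Week 12 sample does not remove that.
- *Every earlier version drew the sample, and subjects passing Week 12 after March 2020 lack it.* The Version 1.1 schedule is not shown. 10 March 2020 is only the version date, and Section 11.2.1 requires ethics approval before subjects enroll under an amendment.

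**Other points against.** Section 7.7.6 defers the ADA analyses to the SAP, and the Section 7.7.1 rule yields to other specifications, so the absence of rules for classifying ADA is no finding. A change between versions is not in itself an error. Neither point replaces a sample that is no longer drawn.

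**Conclusion.** The point holds in a limited form. Version 3.0 removes the PK and ADA samples at RI Week 12/RW Baseline without saying so and offers no substitute. The default RW baselines become 8 weeks old for PK and 6 weeks old for ADA, and no scheduled run-in PK sample is at or after the stated time of steady state. The consequences are an uncertain onset for ADA first seen in RW, in either arm, and the lack of an on-treatment steady-state comparator for about 15.6% of the rilonacept arm.

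That percentage rests on the protocol's exponential model and hazard ratio and on at least 8 weeks of follow-up. The steady-state point carries a finding in CAPS over to recurrent pericarditis. How many subjects lack the sample depends on when each site adopted Version 3.0, which the documents do not give.

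PK and ADA are not efficacy endpoints, so the primary and major secondary analyses and the power are untouched. The correction is still worth making, because the sample cannot be recovered afterwards and the change is small.

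**What to change.** In Version 3.0 Table 2, restore the mark for PK and for ADA in the RI Week 12/RW Baseline column, taken pre-dose within the central blood draw already scheduled at that visit. Use this sample as the RW baseline for both measures. List the correction in the summary of changes. If the removal was intended, that summary should say so and give the reason.

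The cost is extra tubes at an existing clinic visit and a schedule-table amendment.
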